A two-arm pilot RCT (N=100, up to 120 assuming 20% attrition) will test cessation treatment utilization, smoking cessation outcomes, and COPD diagnosis rates as a function of smoking cessation e-visit vs. TAU. Recruitment will primarily occur proactively and remotely via the EMR. We will conduct an automated EMR search via established procedures for all patients treated within MUSC DFM clinics during the past 12 months who: 1) smoke, 2) are ≥ 40 , 3) have MyChart accounts, and 4) do not have COPD on their problem list. **These patients will be sent a MyChart message from a member of their care team inviting them to participate in a research study for cigarette smokers. These messages will only be sent to patients of PCPs who have agreed that their patients may be contacted for the purpose of this study. This invitation will include clear opt out procedures should the patient not wish to be contacted in the future for the purpose of this study. Clinical providers included in the Usability Testing phase of the project will not be asked to directly refer their own patients to the study. However, their patients may still be recruited via the EMR.** After sending these automated e-mail messages via MyChart, the study team may also call, e-mail, and/or text message potential participants to notify them that a message was sent to them via MyChart. Again, such contact will only be made to patients of PCPs who have agreed that their patients may be contacted for the purpose of this study. If interested, participants will complete a screening online via MyChart to determine study eligibility (see above for inclusion criteria). After completing determination of eligibility, if eligible and interested in participating in the study, participants will be scheduled for a time to complete informed consent (see 9.0 Consent Process). After consent is obtained, participants will be randomized 2:1 to receive either the smoking cessation e-visit or TAU. If randomized to the e-visit condition, participants will be sent a link to initiate the e-visit. All e-visit medication recommendations will be reviewed by physicians included on this IRB protocol. Medications will be e-prescribed to a mail order pharmacy (e.g., MUSC's mail order pharmacy) and then mailed to participants, with all costs covered by the study. Note

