that only FDA approved cessation medications will be recommended, which include nicotine replacement therapy (patch, gum, lozenge), varenicline, or bupropion. Medications will only be recommended if a participant does not have a contraindication for that medication. Women who indicate during the e-visit that they are currently pregnant or are planning to become pregnant within the next 6 months will not receive a medication recommendation/prescription as a result of the e-visit. These women will receive a counseling referral. Any woman under the age of 55 who receives a varenicline recommendation as a result of the e-visit will subsequently be asked within the e-visit if she is willing to complete a pregnancy test that will be mailed to her at no cost to verify that she is not pregnant prior to taking varenicline.

Women under the age of 55 who respond “Yes” to this item will be mailed a pregnancy test by study staff and will be required to verify (with signature) that they completed the test and are not pregnant via REDCap. Women under the age of 55 who respond “No” to this item will not receive varenicline as a result of the e-visit. These women instead will either receive NRT, bupropion and/or counseling based on other contraindications and medication preferences indicated throughout the e-visit. Participants will be scheduled for a follow-up e-visit one month following their initial e-visits. The follow-up e-visit may also result in a medication recommendation that will be e-prescribed and mailed to the participant as outlined above for the baseline e-visit. If randomized to the TAU condition, participants will be provided information on quitting smoking, including information about the state quitline, and will be provided a recommendation to contact their PCP to schedule a medical visit to discuss quitting smoking.

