All participants will subsequently be text messaged and/or emailed a REDCap link, accessible via smartphone, tablet, or computer to complete study assessments. These assessments will occur at baseline (following consent), 1-month following study enrollment, and 3-months following study enrollment. Assessments are estimated at 20 minutes each and will be administered remotely via REDCap through our established procedures. Participants will be compensated via electronic gift cards (e.g., Amazon) which will be emailed or texted to participants. Participants will receive \$30 for completion of the baseline assessment questionnaire. After completing each follow-up questionnaire within 72 hours of being emailed the link, participants will be compensated \$30. Participants will be compensated \$30 for each completed carbon monoxide recording. They will be compensated an additional \$100 for completion of all three sets of questionnaires and both carbon monoxide samples. E-visit acceptability and feasibility will be assessed both by examining the percentage of patients who complete the initial and follow-up e-visits, and by participant self-report during follow-up assessments. Participants will respond to items assessing ease of use, satisfaction, and pros/cons of the e-visit. Analytics data (e.g., amount of time it takes to complete the e-visit, amount of time it takes the provider to review the e-visit) will also be collected as will data on provider fidelity to e-visit recommendations (captured by reviewing within Epic

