whether the provider administered treatment consistent with e-visit recommendations). Cigarette smoking, use of other tobacco products (e.g., e-cigarettes), and quit attempts/quit duration will be assessed at each follow-up using a timeline followback for the last 6-months at baseline and since prior follow-up for each subsequent assessment^{7,8}. Nicotine dependence will be assessed at baseline via the Fagerstrom Test of Nicotine Dependence⁹. Participants will report motivation to quit and confidence in quitting using a modified Contemplation Ladder¹⁰. Expired air carbon monoxide will also be captured. Treatment utilization will be assessed via participant self-report. At each follow-up assessment, participants in both groups will be queried for: 1) use of a smoking cessation medication since the last assessment, 2) how the medication was obtained (e.g., via the study or another outlet such as MUSC's existing smoking cessation service), and 3) receipt of the 5As from their PCP⁶. COPD diagnosis will be assessed via participant self-report and via medical records review. At each follow-up time point, participants will be asked whether a clinical provider has given them a COPD diagnosis. Medical records will be reviewed for up to 12-months following completion of the 3-month follow-up survey to identify: 1) whether the participant was referred for in person spirometry, 2) whether the participant attended that appointment, and 3) whether the participant was given a diagnosis of COPD.

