All screening information will be kept in a password protected REDCap database. Only key study personnel will have access to the database. If an individual is not eligible to participate, his/her screener will include his/her first name and last initial and the reason for disqualification. Eligible participants' full name, telephone number and e-mail address will be recorded in the database. This is the only place where participants' names and subject identification numbers appear together. Eligible participants will be assigned a subject number, will complete informed consent, will be randomized, will complete baseline assessments, and subsequently will receive their randomized intervention.

Upon completing eligibility screening, if study eligible, individuals will be provided with an overview of the study, asked to review study procedures via a consent form, and asked to provide signed consent. Participants will be informed of limitations of confidentiality (i.e., abuse or neglect, intention to harm self or someone else) both verbally and/or in writing during the informed consent process. The consent form will include the participant's name, but not his/her subject number. Consent forms will be provided in English. As utilization of the smoking cessation e-visit requires that participants are able to read, participants unable to read the consent form on their own will not be included.

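### Participants are randomised before the self-reported baseline assessment, and the plan does not say that the arm stays undisclosed until baseline is submitted

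*Combined protocol and SAP*

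**What the plan says.** The full order of events appears once, in Section 13.0 under Protections Against Risk: participants "will complete informed consent, will be randomized, will complete baseline assessments, and subsequently will receive their randomized intervention".

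Section 10.0 (Pilot RCT) describes the same steps piece by piece:

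- Randomisation: "After consent is obtained, participants will be randomized 2:1 to receive either the smoking cessation e-visit or TAU".
- E-visit arm: "If randomized to the e-visit condition, participants will be sent a link to initiate the e-visit".
- TAU arm: "If randomized to the TAU condition, participants will be provided information on quitting smoking".
- Assessments, described after the arm procedures: "All participants will subsequently be text messaged and/or emailed a REDCap link, accessible via smartphone, tablet, or computer to complete study assessments".
- Timing: "These assessments will occur at baseline (following consent), 1-month following study enrollment, and 3-months following study enrollment".

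Smoking and quit attempts are collected "using a timeline followback for the last 6-months at baseline and since prior follow-up for each subsequent assessment", and the Fagerstrom test is given at baseline. Section 12.0 (Quality Assurance) plans to check whether the arms are alike at baseline, in case adjustment is needed. Section 11.0 names Fisher's exact tests for the primary smoking-related outcomes and an exploratory GEE of change over time with sex and time as covariates.

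**The concern.** Baseline data are useful for comparing or adjusting arms because allocation cannot have influenced them. That is guaranteed when they are collected before randomisation. When they are collected afterwards, it depends on the participant not knowing the arm when answering.

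Here the arms are easy to tell apart: one offers an e-visit and study-paid medication by mail, the other quit-smoking information and advice to see the PCP. The baseline is completed remotely, and the measures stated for it are the participant's own account of smoking, quit attempts and dependence. Someone who knows the arm might describe past smoking differently, or might be more or less inclined to complete the questionnaire. A baseline value shaped in this way is not a valid adjustment variable, and baseline missingness that differs by arm would make the arms harder to compare.

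**Working it through.** The point rests on the order of events and on no figure in the plan, so the check is a side-by-side reading followed by a short count.

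**1. Is baseline ever placed before randomisation?** No. Section 13.0 puts it after. Section 10.0 goes from consent directly to randomisation, and times baseline only by reference to consent.

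**2. Is the intervention held until baseline is done?** In Section 13.0, yes: receipt of the intervention is the last step. In Section 10.0 the hold is not repeated. Neither the e-visit link nor the TAU information is made conditional on a submitted baseline, and the assessment link is introduced afterwards with an adverb of sequence ("All participants will subsequently be text messaged and/or emailed a REDCap link, accessible via smartphone, tablet, or computer to complete study assessments"). That adverb may reflect only the order of the narrative, so the two sections can be read together. Section 10.0 read alone does not secure the hold.

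**3. Is disclosure of the arm held?** Not stated. No section says when participants are told their allocation, and none describes masking or concealment. Receiving an intervention and learning which one is coming are separate events.

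**4. Which analyses use baseline values?**

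- Primary Fisher's exact tests (Section 11.0): no baseline covariate, so not exposed through adjustment.
- Comparability check and possible adjustment (Section 12.0): exposed. The variables are not named.
- Exploratory GEE (Section 11.0): the named covariates are sex and time. Treatment utilization is asked about at follow-ups, as use since the last assessment, and no baseline utilization item is stated. Only quit attempts could carry a baseline value, and only if baseline is entered as a time point, which the plan does not settle.
- Randomised participants with no baseline: exposed. The plan does not say how they would be handled.

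**5. How many people are concerned?** With 120 randomised at 2:1, 120 × 2/3 = 80 e-visit and 120 × 1/3 = 40 TAU. At N=100 the plan gives 67 and 33. Recruitment allows for 120 − 100 = 20 losses, without saying how many may occur before baseline.

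**6. What discourages skipping baseline?** Section 10.0 pays $30 for baseline, $30 for each of two follow-up questionnaires, $30 for each of two carbon monoxide recordings, and $100 "for completion of all three sets of questionnaires and both carbon monoxide samples". The total is 30 + 2 × 30 + 2 × 30 + 100 = $250. Skipping baseline forfeits 30 + 100 = $130, and 130/250 = 52%. The terms are the same in both arms.

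No step yields a size or direction of bias. That would need the rate of early disclosure and its effect on answers, and the documents give neither.

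**The case against.** The strongest reply is that Section 13.0 already contains the safeguard. The only routes the documents describe by which a participant would learn the arm are the e-visit link and the TAU information. Those are the interventions, and Section 13.0 puts them after baseline. On that reading, earlier disclosure is possible but nowhere planned. This stands in part. It is why the point concerns an unsecured step, and why completing baseline first is simply the safer sequence.

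Two stronger readings are tempting, and the documents support neither. A reader might infer from Section 10.0 that treatment starts before baseline, or that Sections 10.0 and 13.0 contradict each other; the wording in Section 10.0 can be narrative order only. A reader might also infer that the primary comparison is biased; the Fisher's exact tests use no baseline covariate.

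Other replies also have weight. Six-month recall concerns behaviour that almost wholly precedes allocation, and the Fagerstrom test measures established dependence, so reporting could shift but the underlying facts could not. Smoking status for eligibility is screened before consent. Motivation and confidence might be more sensitive to knowing the arm, but no time points are stated for them, so the point does not rest on them. The payments should keep baseline loss low in both arms, though they neither prevent a difference between arms nor affect how questions are answered. Finally, the lack of masking during treatment is inherent in comparing an e-visit with none and is not a separate fault.

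**Conclusion.** The point holds in limited form. The plan randomises before a self-reported baseline, holds the intervention until afterwards in one section only, and does not say that the arm is undisclosed until baseline is submitted. Knowledge of the arm could therefore influence baseline answers or completion.

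The consequence is confined to the Section 12.0 comparability check and any adjustment that follows from it, the exploratory GEE for quit attempts if baseline is a time point, and the number randomised without a baseline. This is a risk and not a demonstrated bias; its size and direction cannot be computed from the documents. It assumes that some participants could learn their arm before submitting baseline, which the plan neither states nor rules out. Severity is minor: a cheap improvement to the sequence.

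**What to change.** In Sections 10.0 and 13.0, set one order: consent, completed baseline REDCap assessment, randomisation, then the e-visit link or the TAU information.

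If the present order is kept, state in both sections that the allocation, the e-visit link and the TAU information are withheld until baseline is submitted, and report by arm the number randomised with no baseline. The recall windows, which run from the prior assessment, need no change.

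The cost is a few words in two sections and a change in the order of steps already planned, with no added visit, questionnaire or contact. The documents do not describe how randomisation is carried out, so any set-up effort is unknown. The downside of reordering is that a few consented people may drop out before randomisation, so slightly more may need to be consented.

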14.0 Potential Benefits to Subjects or Others

All smokers in this trial will receive at minimum standard smoking cessation care and evidence-based educational information about quitting smoking. We will not augment standard smoking cessation care as provided by each patient's primary care physician. The majority of participants will also receive an invitation to complete a smoking cessation e-visit. The major benefit to society will be whether this smoking cessation e-visit will improve cessation outcomes relative to TAU. Potential issues of medication risks,

confidentiality, and frustration are a high priority and will be closely monitored throughout the study. Consequently, the risk to benefit ratio in the proposed study appears to be acceptable.

